### **6.5 Definition of Time to First Ambulation and Hospital Discharge**

Time to first walk is defined as the interval between the end of surgery and the time at which the patient can take at least three steps with a walker under physiotherapist supervision. Length of hospital stay is defined as the number of days from surgery until hospital discharge as decided by the orthopedic surgeon.

## **7. Outcomes and Assessments**

### **7.1 Primary Outcome**

The primary outcome is total morphine consumption (mg) in the first 24 postoperative hours, calculated as the cumulative dose of intravenous morphine administered in the PACU and on the ward up to 24 hours after surgery.

### **7.2 Secondary Outcomes**

To compare intraoperative fentanyl consumption between the three groups.

To compare time to first rescue analgesia postoperatively.

To compare Numeric Pain Rating Scale (NRS) scores at rest and during passive 90° hip flexion at predefined postoperative time points (30 min, 2, 4, 6, 8, 12, 18, and 24 hours).

To assess block failure rate, defined as the requirement for more than one rescue morphine dose in the first postoperative hour.

To compare motor recovery (manual muscle test for quadriceps and iliopsoas, and active hip flexion range of motion) over the first 24 hours.

To compare time to first ambulation and length of hospital stay.

To compare intraoperative hemodynamic profiles (heart rate and mean arterial pressure).

To compare the incidence of block-related complications and morphine-related adverse events (e.g., nausea/vomiting, respiratory depression, hypotension, falls).

To compare block performance time and surgical duration between groups.

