### **6.1 General Anesthesia Regimen**

Monitoring includes ECG, non-invasive blood pressure, pulse oximetry, and end-tidal CO2. Induction is achieved with fentanyl 2 µg/kg IV, propofol 2 mg/kg IV, and atracurium 0.5 mg/kg IV to facilitate tracheal intubation. Anesthesia is maintained with isoflurane 1–1.5% in an oxygen-air mixture (FiO2 0.5) and atracurium 0.1 mg/kg IV every 30 minutes. Ventilation is adjusted to maintain end-tidal CO2 between 30–35 mmHg. Hypotension is treated with crystalloids (0.9% saline and/or Ringer's acetate) and incremental ephedrine 5 mg doses as needed. At the end of surgery, neuromuscular

blockade is reversed with neostigmine 0.05 mg/kg and atropine 0.02 mg/kg IV and patients are extubated after full recovery.

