### **6.3 Intraoperative Analgesia and Monitoring**

Rescue analgesia consists of fentanyl 1 µg/kg IV if mean arterial pressure or heart rate increases more than 20% above baseline values. Hemodynamic variables (heart rate and mean arterial pressure) are recorded at baseline, 5 minutes after intubation, at skin incision, and then at regular intervals throughout surgery.

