## **9. Randomization, Allocation Concealment, and Blinding**

Randomization is based on a computer-generated sequence allocating patients to the three study groups in a 1:1:1 ratio. Allocation concealment is achieved using serially numbered, opaque, sealed envelopes prepared by a study coordinator not involved in patient care. Envelopes are opened only after induction of anesthesia. The anesthesiologist performing the block opens the envelope, prepares and administers the assigned intervention, and has no role in postoperative assessment. Patients, surgeons, ward staff, and outcome assessors are blinded to group assignment. Unblinding is permitted only if necessary for urgent clinical management, and the reason and timing are documented.

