## **11.6 Secondary Outcome Analyses**

Total intraoperative fentanyl dose and other continuous secondary outcomes (such as time to first rescue morphine, time to ambulation, length of hospital stay, block performance time, and surgical duration) will be analyzed using one-way ANOVA for normally distributed data or Kruskal–Wallis test for skewed data, with appropriate pairwise post-hoc tests. NRS pain scores at rest and during movement and motor recovery scores will be analyzed at each time point using Kruskal–Wallis tests with Bonferroni-adjusted Mann–Whitney comparisons. Exploratory repeated-measures analyses (e.g., mixed-effects models) may be used to evaluate time-by-group interactions when assumptions are satisfied. Categorical outcomes, such as adverse event incidence and block failure rates, will be compared using chi-square or Fisher’s exact tests as appropriate.

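### Intraoperative MAP and heart rate are compared between arms after pressor treatment, but ephedrine use is not compared, so the recorded contrast would understate a difference in hypotension

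*Combined protocol and SAP*

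**What the plan says.** Sections 2.2 and 7.2 make intraoperative heart rate and MAP a between-arm secondary outcome: "To compare intraoperative hemodynamic profiles (heart rate and mean arterial pressure"). Section 6.3 sets out what is measured: "Hemodynamic variables (heart rate and mean arterial pressure) are recorded at baseline, 5 minutes after intubation, at skin incision", followed by further readings at intervals during surgery.

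The same variables are managed in both directions.

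- **Low side (6.1):** hypotension is treated with crystalloids and "incremental ephedrine 5 mg doses as needed". No numeric trigger is given.
- **High side (6.3):** fentanyl is given "if mean arterial pressure or heart rate increases more than 20% above baseline values".

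Fentanyl is then an outcome in its own right (7.2: "To compare intraoperative fentanyl consumption between the three groups") and is analysed in 11.6. Ephedrine is mentioned only in 6.1. Neither its dose nor the number of patients who receive it is listed as a recorded variable, an outcome or an analysis, and the same is true of crystalloid volume. The examples of continuous secondary outcomes in 11.6, apart from fentanyl, are "time to first rescue morphine, time to ambulation, length of hospital stay, block performance time, and surgical duration". MAP and heart rate fall under that general rule only by implication, and nothing there refers to treatment received.

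**The concern.** A MAP reading taken after ephedrine reflects both the patient's underlying pressure and the correction. If a block in one arm lowers pressure more often, that arm gets more ephedrine and its recorded MAP is pulled back toward the others. Part of the difference then leaves the variable the plan compares and moves into one it does not.

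The asymmetry is the plan's own. It counts the drug that pulls high values down and does not count the drug that pulls low values up. A report that the three arms had similar intraoperative hemodynamics could therefore be made although one arm needed more pressor support to get there. In patients aged 65 or over and up to ASA III, that is a tolerability difference a reader would want to see.

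**Working it through.** **What can be checked in the text.** The plan states no figure for the hemodynamic comparison: no expected MAP, SD, difference, treatment threshold or ephedrine response. There is nothing to reproduce, so the first check is a side-by-side reading.

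| Direction | Treatment | Treatment compared by arm? |
|---|---|---|
| MAP or heart rate high | Fentanyl (6.3) | Yes (2.2, 7.2, 11.6) |
| MAP low | Crystalloids and ephedrine (6.1) | No |

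The only other cover on the low side is the adverse-event item in 7.2, which includes "morphine-related adverse events (e.g., nausea/vomiting, respiratory depression, hypotension, falls"). Hypotension there has no definition, threshold or time window, and it does not count doses or patients treated.

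**Illustration of size.** Only the 31 per arm (Section 8) comes from the documents. The remaining inputs are assumptions:

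- 12 readings per patient, between-patient SD 8 mmHg, within-patient SD 6 mmHg;
- two arms, comparator mean MAP 78 or 70 mmHg, the other arm truly 6 or 8 mmHg lower;
- a 5 mg dose after any reading below 65 mmHg, adding 8, 12 or 16 mmHg to the next reading's pressure contribution after halving at each reading;
- outcome = each patient's mean MAP, Mann–Whitney test at two-sided 0.05, 1000 simulated trials per setting.

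Share hidden = 1 − (recorded gap ÷ simulated untreated gap). For example, 1 − 4.79/5.96 = 20%, and 1 − 4.13/8.06 = 49%.

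| Comparator MAP | Untreated gap (power) | Lift per dose | Recorded gap (power) | Share hidden | Extra ephedrine per patient |
|---|---|---|---|---|---|
| 78 | 5.96 (0.79) | 8 | 4.79 (0.77) | 20% | 5.1 mg |
| 78 | 5.96 (0.79) | 12 | 4.35 (0.78) | 27% | 4.5 mg |
| 78 | 5.96 (0.79) | 16 | 4.19 (0.78) | 30% | 4.2 mg |
| 78 | 8.07 (0.96) | 8 | 6.25 (0.96) | 23% | 7.7 mg |
| 78 | 8.07 (0.96) | 12 | 5.78 (0.94) | 28% | 6.6 mg |
| 78 | 8.07 (0.96) | 16 | 5.27 (0.94) | 35% | 6.0 mg |
| 70 | 6.10 (0.80) | 8 | 3.98 (0.77) | 35% | 8.6 mg |
| 70 | 6.10 (0.80) | 12 | 3.68 (0.78) | 40% | 7.4 mg |
| 70 | 6.10 (0.80) | 16 | 3.20 (0.74) | 48% | 6.3 mg |
| 70 | 8.06 (0.96) | 8 | 5.34 (0.96) | 34% | 12.0 mg |
| 70 | 8.06 (0.96) | 12 | 4.70 (0.95) | 42% | 9.8 mg |
| 70 | 8.06 (0.96) | 16 | 4.13 (0.94) | 49% | 8.5 mg |

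**Sensitivity to the threshold.** A three-arm version (means 80, 80 and 72 mmHg, lift 8 mmHg, same SDs and number of readings) gave recorded gaps of about 6.6, 5.9 and 5.3 mmHg with treatment below 65, 70 and 75 mmHg. The shares hidden are (8 − 6.6)/8 = 18%, (8 − 5.9)/8 = 26% and (8 − 5.3)/8 = 34%. Power on mean MAP stayed at about 0.97 with or without treatment.

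**Reading of the results.** In every setting the gap shrinks and reappears as extra ephedrine. Power barely moves, because treatment also narrows the spread of MAP. What is lost is mainly the size of the difference, not the ability to detect one.

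**The case against.** Four points can be made for the plan as it stands.

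*Hypotension is already compared.* It is named in the adverse-event outcome, 11.6 supplies a chi-square or Fisher's exact test, and Section 12 records suspected block-related complications from the time of the block, so intraoperative events could be counted. This stands in part: it would be wrong to infer that the plan ignores hypotension. But the item is undefined, and an arm whose pressure is promptly corrected may record few events while receiving more drug.

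*Detection is hardly affected.* This stands. A reader might infer that treatment makes the MAP comparison badly underpowered. That would need a model with a single MAP value per patient, whereas 6.3 calls for repeated readings; averaging them leaves power nearly unchanged. Nor is ephedrine use a sharper test: in the two-arm runs its power was 0.65 to 0.95, never above that of recorded MAP in the same setting. The case for adding it is interpretation.

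*Ephedrine use is itself discretionary.* It is given as needed, and Section 9 says "Patients, surgeons, ward staff, and outcome assessors are blinded to group assignment" without listing the anesthesiologist managing the case. This stands, and is a reason to treat ephedrine use as supportive.

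*The fentanyl outcome.* A reader might also infer that ephedrine raises heart rate, trips the fentanyl trigger and so contaminates the fentanyl comparison. The trigger wording does not exclude this, but nothing in the documents indicates how often it would happen, and block failure is defined by postoperative morphine, not fentanyl.

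**Conclusion.** The point holds as a limited one. The plan compares a treated variable, counts the treatment on the high side and leaves it uncounted on the low side. If arms differ in their need for ephedrine, recorded MAP would understate the difference in hypotension. On assumed inputs the hidden share was about 18% to 49% of a 6–8 mmHg gap, with about 4–12 mg more ephedrine per patient in the affected arm in the two-arm runs. These figures show direction and plausibility only: the true amount depends on the treatment threshold, response and baseline pressures, none of which the documents give.

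The documents do not support the stronger inference that a real difference would be erased; in every run it was shrunk and still visible. This is one secondary outcome among many, and the primary comparison of 24-hour morphine is untouched.

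**What to change.** In 7.2, add two supportive components to the hemodynamic outcome: any intraoperative ephedrine (yes/no) and total intraoperative ephedrine dose (mg), by arm. In 11.6, name the tests: chi-square or Fisher's exact for the first, Kruskal–Wallis for the second. State that hemodynamics will be described as similar only when MAP, heart rate and ephedrine use all point the same way.

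Do not replace readings taken after ephedrine with a lower value, and do not drop fentanyl doses given after ephedrine. Both condition on treatment given after randomization. The first could carry one early low value through the rest of surgery, and the second could discard doses given for real nociception, selectively in the arm with more ephedrine.

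The cost is two extra secondary comparisons, labelled supportive, and some extraction from the anesthesia charts, which Section 10 already names as source documents. No treatment rule changes.

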## **1. Background and Rationale**

Total hip arthroplasty (THA) is widely performed for traumatic hip fractures and degenerative hip disease in older adults and is associated with substantial postoperative pain that can delay mobilization and prolong hospital stay. Effective multimodal analgesia is essential to facilitate early rehabilitation and reduce opioid-related adverse effects in this vulnerable population.

Opioid analgesics provide rapid pain relief but carry important risks in elderly patients, including respiratory depression, delirium, constipation, nausea/vomiting, and prolonged hospitalization. Regional anesthesia techniques, particularly peripheral nerve and fascial plane blocks, are increasingly used as opioid-sparing strategies after THA.

The pericapsular nerve group (PENG) block targets the articular branches of the femoral, obturator, and accessory obturator nerves supplying the anterior hip capsule via local anesthetic injection between the psoas tendon and superior pubic ramus. It has been described as providing effective, largely motor-sparing postoperative analgesia for hip surgery and acute pain after hip fracture.

The anterior quadratus lumborum block (AQLB) deposits local anesthetic in the fascial plane between the quadratus lumborum and psoas major muscles, aiming to block lumbar plexus articular branches and provide analgesia for hip surgery. Previous studies reported favorable analgesic profiles of AQLB in THA.

Both PENG and AQLB appear anatomically capable of covering the operative field in THA, but they may differ in their balance between analgesic efficacy, opioid-sparing effect, and motor impairment. Comparative data between these two techniques in elderly

patients undergoing THA under general anesthesia are limited. This trial evaluates whether ultrasound-guided PENG block or AQLB offers superior postoperative analgesia and functional recovery compared with standard opioid-based analgesia and compares PENG and AQLB directly.

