#### **6.2.3 Control Group**

Patients in the Control group do not receive a regional nerve or fascial plane block. Analgesia is based on systemic opioids only: intraoperative fentanyl and postoperative morphine as described below. A sham dressing may be applied to mimic a block site and maintain blinding.

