## **12. Safety Monitoring**

All serious adverse events and suspected block-related complications will be recorded from block performance until 24 hours postoperatively and throughout the hospital stay. Any severe or unexpected serious adverse event judged related to the intervention will be reported to the institutional ethics committee according to local regulations. Given the limited size and low risk of the study, no independent data monitoring committee is established; safety monitoring responsibilities lie with the principal investigator and the department head.

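### Safety events are defined by presumed cause (block or morphine), and no comparison of each event by randomised arm regardless of cause is specified

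*Combined protocol and SAP*

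**What the plan says.** The only adverse event outcome in the plan is one sentence, the same in sections 2.2 and 7.2: "To compare the incidence of block-related complications and morphine-related adverse events (e.g., nausea/vomiting, respiratory depression, hypotension, falls". It names two classes, each defined by what is thought to have caused the event. The examples follow the morphine class.

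Other sections bear on how the sentence would work:

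- Section 1 says of the two blocks that "they may differ in their balance between analgesic efficacy, opioid-sparing effect, and motor impairment".
- Section 6.2.3: "Patients in the Control group do not receive a regional nerve or fascial plane block".
- Section 9: "Patients, surgeons, ward staff, and outcome assessors are blinded to group assignment". The anaesthesiologist who gives the block takes no part in postoperative assessment.
- Section 11.6 names the test: "Categorical outcomes, such as adverse event incidence and block failure rates, will be compared using chi-square" or Fisher's exact tests. It does not define the adverse event endpoint.
- Section 12 sets what is recorded: "All serious adverse events and suspected block-related complications will be recorded from block performance until 24 hours postoperatively and throughout the hospital stay". It plans no comparison between arms.

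No section gives a rule for attribution, names who attributes, or says where an event with both causes or neither belongs.

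**The concern.** Randomisation protects a comparison of all falls by arm. It does not fully protect a comparison of falls that have first been filtered by a judgement about cause made after allocation.

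Here the filter can act differently by arm. In a block arm, a fall can be put down to the block or to morphine. In Control, only morphine is available. Blinding does not settle this. An assessor who stays blinded does not know whether a block was given and cannot soundly call an event block-related; an assessor who does know attributes with that knowledge. The amount of morphine given is itself the primary outcome and is affected by allocation, so it may also colour a judgement that morphine was the cause.

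At stake is the clarity of the safety side of the trade-off that section 1 describes, between sparing opioids and impairing motor function. The primary analysis is not affected.

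**Working it through.** The plan gives no adverse event rates, so it has no figure of its own to reproduce on this point. The check has three parts: the text, an algebraic check of the labelling, and an illustration on assumed counts.

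**1. The texts side by side.**

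| Question | Where the plan could answer | What it gives |
|---|---|---|
| Which events are compared? | 2.2, 7.2 | Two cause-labelled classes |
| Is there an all-cause endpoint? | 11.6 | A test for unqualified adverse event incidence; no definition |
| Can both classes occur in every arm? | 6.2.3 | No; Control has no block |
| Are non-serious events recorded whatever the cause? | 12 | Not stated; only serious events and suspected block complications |
| Who attributes, and how? | 9, 12 | Not stated |

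**2. What labelling does when the arms do not differ.** Let the true all-cause fall rate be *p* in every arm, and let a share *s* of block-arm falls be labelled block-related. In the order first block arm / second block arm / Control:

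- morphine-related: *p*(1 − *s*) / *p*(1 − *s*) / *p*
- block-related: *ps* / *ps* / 0

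With assumed values *p* = 15% and *s* = 0.5, these are 7.5% / 7.5% / 15% and 7.5% / 7.5% / 0%. Both counts differ between the block arms and Control although the total does not.

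**3. What labelling does when the arms do differ.** Assume 31 per arm (the section 8 target) and all-cause falls of 1 / 6 / 1. The exact test conditions on the total *T* and sums C(31,a)·C(31,b)·C(31,c) / C(93,*T*) over all tables no more probable than the one observed.

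- All causes, 1 / 6 / 1: *T* = 8, P = 0.046.
- If five of the six are labelled block-related, the block-related count is 0 / 5 / 0: P = 3 × C(31,5) / C(93,5) = 3 × 169,911 / 51,971,283 = 0.0098.
- The morphine-related count is then 1 / 1 / 1, with no difference.

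The difference of 5/31 (16.1 percentage points) between the second block arm and Control moves from one count to the other. In the block-related count, however, Control's zero is fixed by definition and is not an observation.

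**4. When events fall in neither class.** Assume all-cause falls of 15% in the two block arms (62 patients) and 5% in Control (31 patients). If a share *q* of the excess is judged to be due to neither cause, the visible difference is 10 × (1 − *q*) points: 10 at *q* = 0, 5 at *q* = 0.5, and 0 at *q* = 1. Power of a two-sided 5% test of the visible difference is 26% at *q* = 0 and 10% at *q* = 0.5. Even the complete count therefore has low power.

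**The case against.** The strongest reply is that nothing need be lost. The sentence compares both classes, so an event that leaves one enters the other. A reader might infer that harm from block weakness can be taken out of the comparison altogether. The documents do not support that: in the example above the relabelled falls reappear as 0 / 5 / 0 and remain visible between the two block arms. Only events judged to be neither would disappear.

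A reader might also infer that total adverse events are not compared at all. That is too firm. Section 11.6 refers to "Categorical outcomes, such as adverse event incidence and block failure rates" with no cause qualifier, and section 12 records every serious event whatever its cause. What can be said is that an all-cause comparison of each event is not specified.

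Other parts of the reply also stand:

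- The list of examples can be read as covering both classes, or simply as event types. If every fall is counted, only the label is imprecise.
- Weakness is measured directly in all arms: "To compare motor recovery (manual muscle test for quadriceps and iliopsoas, and active hip flexion range of motion) over the first 24 hours".
- Blinding of ward staff and assessors reduces differential attribution, though it does not replace a rule.
- Section 1 links the blocks to motor impairment only, so the argument is stronger for falls than for hypotension.
- The counts above are invented and fragile. At 1 / 5 / 1 the exact P is 0.21, and 6 versus 1 of 31 gives a pairwise Fisher P of 0.10 before any Bonferroni correction.

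What the reply does not answer is that the plan leaves open whether attribution will be used as a filter. It also leaves recording of non-serious events outside the suspected block-related class unstated.

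**Conclusion.** The concern holds in a limited form. The only defined adverse event outcome is sorted by presumed cause, no attribution rule is given, and no all-cause comparison of each event by arm is specified. If attribution is used to sort events, ambiguous events are split between two counts, one of which cannot occur in Control, and events judged to be neither are lost. Neither count is then a fully randomised comparison. If every named event is counted whatever its cause, only the wording is at fault.

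The documents do not allow the size to be estimated; the figures above rest on assumed rates and counts. They show that labelling can create or redistribute a difference. They are not evidence that harm would be concealed. This is a minor point about a secondary safety outcome, worth making because the remedy is cheap.

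**What to change.** Reword sections 2.2 and 7.2 along these lines: the incidence of each of falls, hypotension, respiratory depression and nausea/vomiting is compared between randomised arms regardless of presumed cause, with pairwise risk differences and exact 95% confidence intervals; attribution to block or morphine is listed descriptively only. Let section 11.6 refer to those endpoints.

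Add to section 12 that these named events are recorded in all arms whatever their presumed cause. This is needed because the present text commits only to serious events and suspected block complications, so complete capture of the rest cannot be assumed.

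The cost is slightly more recording and one changed table. Power for rare events stays low, which is a reason to report intervals rather than rely on P values.
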